## 3.0 RESEARCH SUBJECT SELECTION

### 3.1 Eligibility Criteria

Eligible patients include women >20 years of age who plan to receive chemotherapy at DFCI to treat recurrent, incurable gynecologic cancers (i.e., ovarian, uterine, and cervical that has recurred despite  $\geq 1$  prior treatments), own a smart-phone (Android or iOS), are capable of downloading and running the study app, can read and provide informed consent in English, and do not have cognitive or visual impairments that would preclude use of the app.

### 3.2 Exclusion Criteria

Patients will be ineligible if they are participating in an investigational drug treatment trial that requires structured symptom or toxicity reporting at the time of enrollment. Patients with severe cognitive impairments or who appear too weak, emotionally distraught, agitated or ill to participate, as judged by either the research study staff or an oncology provider, will be excluded. Patients who are unable to provide informed consent in English will be excluded because the smartphone app intervention is only available in English at this time. Children and young adults up to age 20 will be excluded because the diagnosis of metastatic gynecologic cancers in this age group is rare and the proposed instruments are not designed for people of those ages. In addition, patients with a life expectancy of  $\leq 6$  months, as determined by their oncology providers, will be excluded since they cannot participate in all of the required data collection. Patients who are currently actively tracking their steps using wearable technology or smartphone apps will also be excluded.

## 4.0 RESEARCH SUBJECT ENTRY

### 4.1 Subject Recruitment and Enrollment

We will enroll patients from the DFCI Gynecologic Oncology Program. Study staff, gynecologic oncology providers, and members of the Gynecologic Medical Oncology Team will identify patients who may be eligible for the study. Prior to initiating recruitment, we will meet with the clinical staff, including oncologists, embedded palliative care physicians, nurse practitioners, program nurses, clinical research study staff, and social workers, to discuss and solicit feedback on the recruitment and enrollment procedures.

#### 4.11 Screening & Recruitment

Prior to obtaining informed consent, study staff will review the electronic medical records of patients listed on the gynecologic oncology providers' clinic schedules to identify patients with metastatic, recurrent gynecologic cancers undergoing chemotherapy. These patients' medical records will only be reviewed to confirm this protected health information (PHI), and it will only be shared with gynecologic oncology providers in the context of patients' eligibility for the study.

When an eligible patient is identified, study staff will contact the patient's oncology provider to confirm she meets the eligibility criteria and to request permission to approach the patient at an upcoming clinic visit. If the patient is approved to approach for enrollment, the research assistant (RA) will coordinate with the oncology provider to meet with the patient to discuss the study at the time of her clinic visit. If the

oncology provider deems the patient ineligible or too distressed to participate in a clinical study at this time, the patient will not be approached for inclusion.

PHI will not be shared with anyone outside of the study team and patients' oncology providers. All emails will be sent within the Partner's firewall. A HIPAA waiver requesting permission to review the PHI of these select patients prior to consent during screening and recruitment has been submitted to justify this process.

#### 4.12 Informed Consent

If a patient agrees to learn more about the study, the RA will meet with the patient to describe the study, review the consent form, answer any questions, and provide her contact information. The RA will encourage patients to take their time in deciding whether they want to participate in the study or not.

If a patient is interested in participating, the RA will obtain written informed consent, which will include explaining how and why the current research study is being conducted, the study risks and benefits, the potential time commitment involved, and the option to give permission to be contacted for future research studies. The RA will explain in explicit detail what type of information will be collected from the smartphone application and wearable accelerometers and how these data are monitored. The RA will reiterate that the data collected are not a part of the patient's standard treatment and will underscore the importance placed upon maintaining patient confidentiality and a patient's rights while involved in the study, including the right to withdraw participation at any time for any reason during the study because participation is completely voluntary.

The informed consent form will contain a section dedicated to explaining what constitutes PHI and how this information will be protected as confidential per HIPAA guidelines. The consent form will also provide contact information for both the Principal Investigator (PI) as well as the Office for the Protection of Research Subjects. All informed consent processes will adhere to the policies set forth by the Institutional Review Board. Signed informed consent forms will be stored in a locked file cabinet to maintain the privacy of all study participants.

If a patient is unsure if she would like to participate in the study, she will be offered the consent form to review and a postage paid *opt-out card* (Appendix A) to notify study staff that she is not interested. If no contact is made after a few days, the RA will call the patient. If the patient decides to participate, the RA will meet her at a subsequent appointment to obtain informed consent. If a patient is not interested, the RA will thank her for considering, reassure the patient that the process will have no impact on her care. No further interactions will occur with patients who either decline or prove ineligible for the study. Patients will not be contacted after three unreturned voicemails.

#### **4.2 Subject Registration and Randomization**

During both phase I and phase II of the study, the RA will register eligible participants in the Clinical Trials Management System (CTMS) OnCore. Registrations will occur prior to beginning study interventions. Any participant not registered to the protocol before study interventions have begun will be considered ineligible and registration will be denied. An investigator will confirm eligibility criteria and a member of the study team will complete the protocol-specific eligibility checklist.

Following registration, participants may begin study interventions. Issues that would cause delays in interventions should be discussed with the Overall Principal Investigator (PI). If a participant does not receive study interventions following registration, the participant's registration on the study will be canceled. Registration cancellations will be made in OnCore as soon as possible. After obtaining informed consent, participants will be assigned a unique study ID and registered to the study in Redcap.

The following information will be recorded for each participant in the *Registration Form* (Appendix B):

- Name and telephone number of RA enrolling the participant
- Date participant signed consent and RA who obtained consent
- Participant's study ID and first and last initials
- Participant's date of birth
- Participant's primary oncology providers
- Confirmation that participant meets eligibility criteria
- Name of oncology provider who approved participant's eligibility and date of approval
- Participant's contact preferences (phone call, text, or e-mail; collected post-consent)
- Participant's study arm (to be completed after randomization)

In the second phase, the study team will randomize enrolled participants to one of the four arms: 1) Fitbit+active app, 2) Fitbit+passive app, 3) Active app, or 4) Passive app —using a 1:1:1:1 ratio using a computer-generated random allocation sequence with blocks of 8 in order to maintain balance between study arms over time. Study staff will generate group assignments in sequentially numbered and sealed opaque envelopes. Please refer to the protocol schema for details.

[figure not shown]

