### 5.5.1 Instrument Administration

#### Participant Baseline Interview:

- The RA will administer the survey to participants via an in-person interview on Day 0 before or after the participant's visit with her oncology provider (Baseline Visit).
- Participants will complete the interview on the same day informed consent is obtained; if this is not possible, the RA and participant will plan to complete it at a subsequent visit.
- Participants will not be asked to come to Dana-Farber outside of their regularly scheduled visits.
- Estimated time to completion: 45 minutes.

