## 5.52 Intervention Administration

### **5.52a Smartphone App**

#### Instructional Session (*passive and active app*):

- Following the completion of the Participant Baseline Survey on Day 0, study staff will help participants download, install, and run the HOPE App on their personal smartphones.
- Participants will be prompted by Android or iOS to agree to install the app and the software will review what the app will have access to on the phone (see the participant guide). This language is part of the Android and iOS operating systems and cannot be changed. There is no way to prevent this message, which is a basic security feature in Android and reflects the broadest possible access granted to an application.
- To ensure that subjects are not misinformed, the study staff member will explain the app's privacy and data security in the *HOPE App Required Reading & Discussion* document (Appendix N). It should be noted that the discussion related to access on page 3 is specific to Android phones only.
- When the app opens, participants will register using a unique User ID and temporary password and then choose a new password. The subject will be assigned a unique 8-character Participant ID which consists of a mixture of numbers and letters. The app does not ask the subject to enter any personal information (name, date of birth, phone number, etc.) and cannot be directly linked to their DFCI health records.
- Participants will enter their oncology providers' phone numbers for the "Call my Clinician" button and enter the RA's contact number for the "Call Research Assistant" button.
- At the end of the registration process, the participant will click a button to acknowledge she has reviewed the information with the RA and provide in-app consent.
- The RA will then review how to use the app and participants will be given a copy of the *HOPE App Participant Guide-Active App* (Appendix O) or the *HOPE App Participant Guide—Passive App* (Appendix W) which describes the app and provides directions on how to use its features, frequently asked questions, as well as a review of the data that is collected and privacy measures.

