## 6.5 Handling of Missing Data

For the primary quality-of-life analysis, we will exclude from our analyses any patients who do not complete any post-baseline EQ-5D questionnaires and carry forward the last post-baseline observation available for patients without 6-month data. If >10% of participants have missing data from the 6-month survey, we will perform sensitivity imputation analyses including: 1) no observations carried forward, 2) minimum observation values carried forward, 3) average observation values carried forward, and 4) last observation carried forward, but with an EQ-5D value of 0 if death occurred before 6 months.

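### HOPE section 4.2 cancels the registration of participants who never receive the intervention, with no exception for Phase 2 patients already randomised and no statement that they are still followed and analysed

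*Combined protocol and SAP*

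**What the plan says.** The registration paragraphs of HOPE section 4.2 cover both phases: "During both phase I and phase II of the study, the RA will register eligible participants in the Clinical Trials Management System (CTMS) OnCore". They go on: "If a participant does not receive study interventions following registration, the participant's registration on the study will be canceled". Cancellations are to be entered in OnCore promptly. The only softening is that causes of delay should be discussed with the overall principal investigator.

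The same section places randomisation after enrolment: "In the second phase, the study team will randomize enrolled participants to one of the four arms". The study arm is added to the registration form once randomisation has taken place.

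Delivery comes later still. Section 5.52a says: "Following the completion of the Participant Baseline Survey on Day 0, study staff will help participants download, install, and run the HOPE App". The baseline interview is meant for the day of consent, but section 5.5.1 adds: "if this is not possible, the RA and participant will plan to complete it at a subsequent visit".

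Section 6 defines no intention-to-treat or other analysis population. The one exclusion that it states for the primary analysis is in section 6.5: "we will exclude from our analyses any patients who do not complete any post-baseline EQ-5D questionnaires". Section 5.53d says that participants will not be censored, but this concerns later enrolment in a therapeutic drug trial only.

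**The concern.** Cancelling a registration for non-receipt is harmless in a single-arm phase. In a randomised phase it selects patients by something that happens after allocation. A woman who is randomised and then becomes too ill to install the app, or declines everything on learning her arm, has received no study intervention and falls under the rule.

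Starting may differ by arm. Arm 1 sets up the HOPE app, the Fitbit app and the device, while arm 4 installs one app that runs in the background. Arm 4 alone also receives a gift card after the baseline interview. The protocol itself sees differential drop-out by arm as a threat (section 5.54), but the 1-, 3- and 6-month incentives given to all arms come after the point at which cancellation would occur.

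If non-starters have a worse outlook and are more common in one arm, removing them flatters that arm on EQ-5D change. Utilisation is affected as well, although chart abstraction could supply those data for a patient who completes no questionnaire. Nor is the trial committed to reporting non-receipt by arm, which is useful information for a pilot whose stated aims include feasibility.

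**Working it through.** **Inputs from HOPE section 6.2.** SD of 6-month change 14 points; 25 patients per arm, so 50 v 50 for each factorial main effect; one-sided 5% test (critical value 1.645); stated power 70% at 6 points and 80% at 7.

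**The plan's own figures.** SE = 14 x sqrt(1/50 + 1/50) = 2.8. Power = Phi(effect/2.8 - 1.645).
- 6 points: Phi(2.143 - 1.645) = 69.1%, against 70% stated.
- 7 points: Phi(2.5 - 1.645) = 80.4%, against 80% stated.

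The figures reproduce only with all 100 patients analysed, so there is no allowance for cancelled registrations.

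**Does the rule reach randomised patients?** Section 4.2 names both phases, randomises participants already enrolled, and exempts nobody. Delivery follows the baseline interview. The text therefore permits cancellation after allocation. How long that window lasts is not stated.

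**Bias formula.** Let u1 and u0 be the shares who never start on the active-app and passive-app sides, and let d be the number of points by which never-starters would have changed worse than starters, taken as the same on both sides. Dropping never-starters raises a side's mean by u x d, so the contrast is biased by (u1 - u0) x d.

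**Assumptions (the documents give no uptake rates).** u1 = 10-20%, u0 = 2-4%, d = 5-15 points. One-sided error = 1 - Phi(1.645 - bias/SE), here with SE = 2.8.

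| Case | u1 | u0 | d | Bias (points) | One-sided error |
|---|---|---|---|---|---|
| Lowest | 10% | 4% | 5 | 0.06 x 5 = 0.3 | 6.2% |
| Midpoints | 15% | 3% | 10 | 0.12 x 10 = 1.2 | 11.2% |
| Highest | 20% | 2% | 15 | 0.18 x 15 = 2.7 | 24.8% |
| Equal shares | 15% | 15% | 10 | 0 | 5.0% |

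With the smaller retained sample at the midpoints (42.5 v 48.5), SE = 14 x sqrt(1/42.5 + 1/48.5) = 2.94 and the error is 10.8%. In the highest case (40 v 49), SE is 2.98 and the error 23.0%.

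**A second set of assumptions.** Shares of 10% v 5% with d = 7 give a bias of 0.35 points and 6.4% error. Shares of 20% v 5% with d = 14 give 2.1 points and 17.2%, using the retained sample sizes in both cases.

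**The case against.** Several arguments count against a strong reading, and most of them stand.

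- **Registration is not analysis.** A reader might infer that a cancelled patient leaves the trial and is beyond recovery. The rule speaks of the OnCore registration. Participants are also registered in REDCap, where interview and chart data are held, and cancelled registrations are not among the exclusions in section 6.5. Loss from follow-up and analysis is an inference from silence. Even so, a cancelled study registration gives no clear basis for continued follow-up, and nothing says that follow-up continues.
- **The trigger is narrow.** A reader might infer that only patients who adhere to their arm are kept. The documents do not say so. Patients who stop sending data are contacted, or receive no summary sheet, and cancellation is not mentioned. A woman who installs the app but declines the Fitbit has received a study intervention. The burden of daily surveys comes after receipt and cannot trigger the rule.
- **All arms are exposed.** A reader might infer that only the heavier arms lose patients. All four arms install an app with staff help, and the same rule applies to each. For the app contrast (arms 1 and 3 v 2 and 4), the apps share one platform and one type of installation session, and Fitbit set-up is balanced. Eligibility already requires the ability to run the app. Differential non-starting is possible but not shown.
- **Timing is unknown.** The documents do not say whether the envelope is opened before or after a delayed baseline interview. If after, the window may be a single session.
- **Overlap with section 6.5.** Some never-starters would provide no post-baseline EQ-5D and would be excluded anyway, so the EQ-5D bias due to section 4.2 alone is smaller than tabulated. This does not help the utilisation outcomes.
- **Non-uptake is not hidden.** Cancellations are recorded in OnCore and could be counted. What is missing is a commitment to report them by arm.

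**Conclusion.** The concern holds as a gap in the text. Section 4.2 permits registration to be cancelled after randomisation for patients who never start, and no section says that they are kept, followed or analysed. The documents do not establish that such patients will be lost, how many there will be, or that they will come mainly from particular arms.

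The size rests wholly on assumed rates: a bias of 0.3 to 2.7 points in the app effect on EQ-5D, and 1.2 points with about 11% one-sided error at the midpoints. It is zero if non-uptake and prognosis are equal across arms. Against a 6-point target in a pilot with 25 patients per arm, this should be fixed, but it does not by itself undermine the trial.

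**What to change.** In HOPE section 4.2, add for Phase 2:

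- Registration may be cancelled for non-receipt of the intervention only before the allocation envelope is opened.
- Every randomised participant stays registered, is followed at 30, 90 and 180 days and by chart abstraction unless she withdraws consent, and is analysed in her assigned arm, subject to the missing-data rules of section 6.5.
- Non-receipt is reported by arm as a feasibility outcome.
- The envelope is opened after the baseline interview, on the day of installation.

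The last item shortens the window and should keep the number of never-starters small. The cost is a paragraph of protocol text, a few more patients to follow, and some dilution of the effect. As an illustration, suppose 10% never start, the effect is 6 points in starters, and never-starters on the intervention side gain nothing. Keeping all 50 per side gives a diluted effect of 6 x 0.9 = 5.4 points and 61.2% power, against 65.1% if 10% on each side are dropped without replacement. At 20% the figures are 52.8% and 60.7%. That loss is the price of an unbiased randomised comparison, and it is small if few patients fail to start.

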## **Protocol Organization for DF/HCC Protocol 16-477**

The protocol document contains the study procedures for the HOPE Trial and the SMART Study. The SMART Study is a sub-study of the HOPE Trial. Both studies evaluate *an almost identical intervention* using a Fitbit device and smartphone app(s) with the goal of improving quality-of-life for women with gynecologic cancers. However, the studies are designed to assess different research questions, and there are slight variations in the interventions being administered: the HOPE Trial is a randomized controlled trial designed to test changes in health-related quality of life at an NCI-designated Comprehensive Cancer Center (DFCI), while the SMART Study is a single-arm study designed to test the feasibility and acceptability of a combined intervention (Fitbit device and two smartphone apps) in NCORP community oncology sites.

Because the interventions tested are similar and only minor variations exist in study procedures (e.g., in timings of outcomes assessments), the studies are being reviewed under one IRB protocol at Dana-Farber Cancer Institute.

The HOPE Trial is being conducted only at Dana-Farber Cancer Institute. *No outside sites are participating in the HOPE Trial.* The HOPE Trial (Phase 2) is a four-arm randomized controlled trial testing Fitbits and a smartphone app. The primary endpoint of Phase 2 of the HOPE Trial is health-related quality of life.

The SMART Study is being conducted only at outside community oncology sites. *Dana-Farber Cancer Institute is not enrolling patients in the SMART Study.* The SMART Study is a single-arm study testing a Fitbit and two smartphone apps (Beiwe and SMART). Primary endpoints for this study are feasibility and acceptability of the intervention in the community oncology sites.

[figure not shown]
To facilitate protocol implementation and regulatory review at both Dana-Farber and outside sites, this document is separated into two sections. Part 1 is the protocol for the HOPE Trial conducted at Dana-Farber only; Part 2 is the protocol for the SMART Study conducted at community oncology sites only. Lettered appendices (Appendices A-Z and AA) correspond with the HOPE Trial; numbered appendices (Appendices 1-24) correspond with the SMART Study.

The HOPE Trial section begins on p.2 of this document. The SMART Study section begins on p. 41 of the document.

[figure not shown]

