### 6.2 Sample Size and Statistical Power or Precisions

A convenience sample of 10 patients will be enrolled to the first phase of the study. Due to the limited sample size, statistical analysis will be descriptive in nature.

100 patients will be enrolled to the second phase of this study, which will employ a 2x2 factorial design as depicted in the table below. Patients will be randomized 1:1:1:1 to one of the four arms.

Fitbit	App	Arm	Sample size
+	Active	1 (Fitbit + active app)	25
+	Passive	2 (Fitbit + passive app)	25
-	Active	3 (Active app)	25
-	Passive	4 (Passive app)	25
		Total	100

For the outcome of change in EQ-5D, we will use a one-sided type I error rate of 5% to conclude that an intervention is promising for further study. Based on prior literature, the standard deviation of the change in EQ-5D at 6 months compared to baseline is approximately 14 points. With a total sample size of 100 patients (25 patients per arm), the table below summarizes the power to conclude that the either or both of the interventions are promising for further study based on a variety of effect sizes.

Difference in EQ-5D versus Usual Care			Power to conclude that intervention is promising for further study	
HOPE App	Wearable accelerometer	HOPE App + Wearable accelerometer	HOPE App	Wearable accelerometer
6	0	6	70%	--
7	0	7	80%	--
6	3	9	70%	28%
7	3	10	80%	28%
6	3	8	62%	23%
7	3	8	68%	17%

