### 6.3 Intervention Allocation Plan

In the second phase, enrolled participants will be randomized to one of the four arms: 1) Fitbit + active app, 2) Fitbit + passive app, 3) Active app, 4) Passive app—using a 1:1:1:1 ratio. Enrolled participants will undergo a secondary randomization to being encouraged to use a smartphone, or not encouraged to use a smartphone. Randomization to the main study arms will occur using a computer-generated random allocation sequence with blocks of 8 in order to maintain balance between study arms over time. Study staff will generate group assignments in sequentially numbered and sealed opaque envelopes.

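### HOPE Phase 2 publishes one fixed block size of 8 and does not separate whoever prepares the sequence from those who recruit, so up to one allocation in seven could be deduced in advance

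*Combined protocol and SAP*

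**What the plan says.** Section 4.2 (Subject Registration and Randomization) allocates 1:1:1:1 by a "computer-generated random allocation sequence with blocks of 8". Section 6.3 (Intervention Allocation Plan) repeats the block size. Neither section mentions a second block size or stratification.

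On who does the work, Section 4.2 states that "the study team will randomize enrolled participants to one of the four arms". Both sections add: "Study staff will generate group assignments in sequentially numbered and sealed opaque envelopes". No independent statistician or central service is named, and nothing bars the person who prepares the envelopes from recruiting.

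The introductory section on protocol organization states: "The HOPE Trial is being conducted only at Dana-Farber Cancer Institute". There is therefore one sequence at one site. Section 6.2 gives the size: "100 patients will be enrolled to the second phase of this study".

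The term open-label is not used, but the arms cannot be masked from staff. Sections 5.52a and 5.52b have staff install the active or passive app and set up the Fitbit, and the visit summaries differ by arm. The Registration Form in Section 4.2 records the arm after randomization, alongside the enrolling research assistant.

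**The concern.** Sealed, numbered, opaque envelopes prevent anyone from reading the next assignment. They do not prevent anyone from working it out. With a single known block size, one sequence and visible arms, the assignments already made in a block reveal those that remain.

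Foreknowledge matters here because entry involves judgement. Section 3.2 lets research staff or an oncology provider exclude a patient who seems too unwell or distressed, and such an impression may well relate to later quality of life. Study staff screen clinic lists (Section 4.11). The research assistant obtains consent (Section 4.12) and also administers the interviews (Section 5.5.1) that yield the self-reported primary endpoint, the EQ-5D.

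If foreknowledge influenced who was approached and when, the arms could differ in unmeasured frailty. The t tests in Section 6.4 would not correct that. The covariates listed for the regression (age, sex, cancer type, race, education, literacy and numeracy) do not include performance status.

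**Working it through.** The documents give no predictability figure to reproduce. As background, the power in Section 6.2 does reproduce. With 50 v 50 patients, SD 14 and one-sided 5%, power = Φ(δ/(14√(2/50)) − 1.645) = Φ(δ/2.8 − 1.645). This gives 69.1%, 80.4% and 28.3% for δ = 6, 7 and 3, against the stated 70%, 80% and 28%. Block size does not enter these figures.

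**Inputs.** Block size 8 (Sections 4.2 and 6.3); four arms at 1:1:1:1, hence two slots per arm per block; N = 100 (Section 6.2). The observer is assumed to know the block size and the start of the sequence, and to have recorded every assignment. The blocking of the secondary smartphone-encouragement randomization is not described and plays no part here.

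**1. Exact arm, complete block.** An allocation is certain when all remaining slots belong to one arm.
- 8th position: probability 1.
- 7th position: the last two slots are the same arm, 4/C(8,2) = 4/28 = 1/7.
- Positions 1 to 6: probability 0, because at least three slots remain and no arm has more than two.

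The expected number per block is 1 + 1/7 = 8/7. The share is (8/7)/8 = 1/7 = 14.3%. A simulation of 400,000 blocks also gave 14.3%.

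**2. Exact arm, this trial.** 100 = 12 × 8 + 4. The last four patients fill positions 1 to 4 of a block, where nothing is certain. The expected number is 12 × 8/7 = 13.7 of 100.

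**3. App factor (active v passive), complete block.** There are four slots on each side. With r slots left, the probability that all are on one side is:
- r = 1: 1
- r = 2: 2·C(4,2)/C(8,2) = 12/28 = 3/7
- r = 3: 2·C(4,3)/C(8,3) = 8/56 = 1/7
- r = 4: 2/C(8,4) = 2/70 = 1/35

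The sum is 8/5 per block, or 20%. The Fitbit factor gives the same figure. Over 100 patients this is 12 × 8/5 = 19.2.

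**4. Best guess.** At each draw the observer names the arm with most slots left. Exact recursion gives 1579/420 correct per block of 8, or 47.0%, against 25% by chance. For active v passive it is 66.6%, against 50%. Over the 100 patients, with the incomplete last block, these are about 46% and 66%.

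**5. An illustrative mixed scheme.** Take five blocks of 8 and five of 12 in random order (5 × 8 + 5 × 12 = 100). The observer knows this composition but not the order. Both sizes are assumptions and do not come from the documents. The values below are simulated, except that the certain share for fixed blocks also follows from step 2.

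| Scheme, N = 100 | Arm certain | Best guess, arm | Best guess, app |
|---|---|---|---|
| Fixed 8 | 13.7% | about 46% | about 66% |
| Five 8s + five 12s | 5.8–5.9% | about 45% | about 65% |

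Drawing 8 or 12 independently at random each time gives 4.5–4.8% certain. That is a different scheme, and it does not fix the total at 100.

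**6. Arm sizes under the present scheme.** Twelve complete blocks give 24 per arm, and the last four patients add 0 to 2 to each, so arms number 24 to 26. The worst split for a factorial comparison is 52 v 48. By the noncentral t, power for a 7-point difference is then 79.8%, against 79.9% at 50 v 50.

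**The case against.** The best defence is that concealment is specified and the route to bias is assumed. The sequence is computer-generated, and 8 is twice the smallest possible block for four arms. The oncology provider confirms eligibility and permits approach (Section 4.11). An investigator also confirms eligibility, and the provider's approval is recorded (Section 4.2). Section 5.12 describes consecutive patients. Approach is tied to clinic visits and undecided patients may consent later, which makes it hard to steer a given patient into a given slot. This is also a pilot. All of this stands. It lowers the likelihood of exploitation but leaves the predictability in place.

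The limit on the remedy also stands. Mixing block sizes reduces certain allocations but hardly changes general guessability, as step 5 shows.

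A reader might infer three stronger things that the documents do not support:

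- **That the recruiter prepares the envelopes.** Study staff is a generic term. The protocol assigns consent to the research assistant and does not say who among the staff prepares the envelopes. The separation is unspecified; a conflict is not stated.
- **That one allocation in seven was, or will be, foreseen.** That needs someone who knows where blocks begin, logs every arm in order and acts on it. No such conduct is documented, and no bias in EQ-5D points can be estimated.
- **That the design matters because 100 is not a multiple of 8.** Section 6.2 tabulates 25 per arm, which blocks of 8 do not guarantee, but the effect on power in step 6 is negligible. Even a scheme that totals 100 would not secure 25 per arm, because Section 4.2 cancels the registration of participants who receive no intervention.

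**Conclusion.** The point holds as a cheap improvement to a stated rule. It is not an arithmetic error and does not invalidate the trial. A single published block size, one unstratified sequence at one site, visible arms and no stated separation of generator from recruiter together allow up to 1/7 of allocations in complete blocks to be known beforehand (13.7 of 100 patients), and 20% for either factor alone.

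These are ceilings for an observer with complete knowledge, and actual exposure may be far smaller. The conclusion rests on reading blocks of 8 as one constant size and on inferring from the procedures that staff know the arms. It merits action because selection on unmeasured frailty could not be repaired in the analysis, while preventing it costs almost nothing.

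**What to change.** In Sections 4.2 and 6.3:

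- State that a statistician, or another person who does not screen, consent or enrol, generates the sequence, prepares the envelopes and holds the list.
- Replace the single block size with mixed sizes in random order, for example five of 8 and five of 12.
- Move the block sizes to a restricted randomization document and say in the working protocol only that blocks of varying size are used.

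The cost is a regenerated list and a named holder outside the recruiting team, with no added patients or visits. The drawback is slightly looser balance part-way through accrual. REDCap is already used for registration and data, but the documents do not describe it as an allocation tool, so using it for that purpose would need checking. If allocation has already begun, only the unused part of the sequence can be changed.
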